6 INTRODUCTION

6.1 Background

Coenzyme Q10 (CoQ10) is a substance similar to a vitamin. It is found in every cell of the body. The body produces CoQ10, and the cells use it to produce energy for the body needs for cell growth and maintenance. It also functions as an antioxidant, which protects the body from damage caused by harmful molecules. CoQ10 is naturally present in small amounts in a wide variety of foods, but levels are particularly high in organ meats such as heart, liver, and kidney, as well as beef, soy oil, sardines, mackerel, and peanuts.

The Coenzyme Q10, also known as ubiquinone, is an endogenous molecule, synthesized by our body and essential for the proper functioning of the mitochondria, or the cellular units responsible for the production of energy in the body.

In organisms it participates in redox reactions and, depending on the state of oxidation, it can be present in three forms: an oxidized, a semi-quinone intermediate and a reduced form. The side chains make it very lipophilic, in fact it is present in biological membranes, especially mitochondrial ones.

Higher levels of Q10 could improve the efficiency of the electron transport chain, increasing the available energy.

Rebalancing the function of the mitochondria, which are in practice the "lungs" of every single cell, means allowing the cell to restore its original energy potential, and, in a certain sense, to "rejuvenate" allowing it to "breathe" and use the available energy correctly.

If coenzyme Q is reduced by acquiring an electron it forms a radical called ubisemichinone (QH.). For further reduction the compound becomes a ubiquinol (QH2).

The concentration of coenzyme Q10 tends to decrease with aging; low levels are also recorded in the presence of particular chronic diseases, such as those resulting from heart problems, Parkinson's disease, muscular dystrophy, diabetes, cancer and AIDS. Certain drugs, such as statins used in the control of hypercholesterolemia, can also lower Coenzyme Q10 levels.

Coenzyme Q10 has been shown to have beneficial effects on some patients with migraine and is a major component of the myth cocktail used in the treatment of mitochondrial myopathy and other metabolic disorders.

Taking 100 mg a day or more of CoQ10 has caused mild insomnia in some people. And research has detected elevated levels of liver enzymes in people taking doses of 300 mg per day for long periods of time. Liver toxicity has not been reported.

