Other reported side effects include rashes, nausea, upper abdominal pain, dizziness, sensitivity to light, irritability, headache, heartburn, and fatigue.

Medicines for high cholesterol (statins) and medicines that lower blood sugar cause a decrease of CoQ10 levels and reduce the effects of CoQ10 supplements. CoQ10 can reduce

	Study Title	Bioavailability Study of COQUN ORAL FORMULATION (CoQ10) administered in Healthy Adults (CoQ10-01)		
	Study ID	VF-BAQ10/2018	Sponsor:	VISUFARMA SpA
	Date	March 03, 2018	Vers.	Final

the body's response to the blood thinner (anticoagulant) medicine warfarin (Coumadin) and can decrease insulin requirements in people with diabetes.

Many factors can affect the Q10 blood level of people who are not taking a Q10 supplement: age, diet, disease, medications (for example, statin medications).

Q10 levels in the blood from the body's own synthesis of the substance increase after (0.20 ug/ml) birth until about the age of 21. Thereafter, the body's synthesis of Q10 gradually decreases.

It is expected that supplementing regularly with Q10 to raise the Q10 blood level, but much depends on the way in which the Q10 product has been prepared and much depends on the dosage. It was demonstrated that taking 30 milligrams or 50 milligrams of Q10 daily will not raise the Q10 level as much as taking 100 mg of Q10 daily will do, while taking 100 milligrams of Q10 twice daily will yield even greater gains in Q10 blood levels.

From the literature it is known that a well-absorbed Q10 supplement should over time raise the blood level to about 2.5 micrograms per milliliter if the individual is taking a 100-milligram dosage once a day, while if taken the same Q10 supplement in a dosage of 100 milligrams twice a day, its blood level should, over time, raise the steady-state Q10 blood level to somewhere in the area of 3.5 micrograms per milliliter. But, the attainable levels will vary from individual to individual, beside depending on the product itself as formulation.

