7.2 VARIABLES

Primary Variable

Pharmacokinetic properties:

- Area under the curve (microg/ml x h): ≥ 5
- Cmax: $\geq 0,8$
- Tmax: ≥ 3
- elimination half-life (t 1/2)

Secondary Variable(s)

The secondary variables are the ones regarding safety which will be monitored through vital signs, physical exams, ECGs, clinical laboratory tests and adverse events, as follows:

- following a single oral dose of 100mg COQUN ORAL FORMULATION
- in 1 month period of daily oral intake of 100mg OD or BID COQUN ORAL FORMULATION

Symptoms and signs like mild insomnia, elevated levels of liver enzymes, rash, nausea, upper abdominal pain, dizziness, sensitivity to light, irritability, headache, heartburn, and fatigue will be closely monitored.

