9.6 Methods of Assigning Subjects to Treatment Groups

Subjects who are eligible for the study will first be thoroughly informed about the aims and details of the study and in case the subject accepts to participate, the signed Informed Consent will be obtained, and the patient will receive the lowest screening number available.

If all required criteria for admitting a subject to the study are fulfilled, the investigator will proceed with the study procedures of the Screening visit (V1) and with the single dose administration of IP.

After the screening visit, subjects will have one week of wash-out period, then will be requested to return to the site for V2, during which Subjects will be randomly assigned to one of the two groups:

- group A: 12 adult healthy subjects will be given OD 100mg of COQUN ORAL FORMULATION, to be taken after dinner
- group B: the other 12 adult healthy subjects will be given BID a dose of 100 mg of COQUN ORAL FORMULATION, to be taken after lunch and after dinner

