10.5.2 Ambulatory visit V2, Day 0 (multidose phase)

Subjects will return at site for entering the multidose phase and will be randomly divided into two groups of treatment:

- group A: 12 adult healthy subjects will be given OD 100mg of COQUN ORAL FORMULATION, to be taken after dinner
- group B: the other 12 adult healthy subjects will be given BID a dose of 100 mg of COQUN ORAL FORMULATION, to be taken after lunch and after dinner;

Plasma coenzyme Q10 will have to be measured over the next 4 weeks.

During V2 the following study procedures will be done:

- vital signs (blood pressure, heart rate, temperature and respiratory rate)
- blood sampling for pharmacokinetic determination
- safety laboratory analysis
- record of concomitant medication
- adverse events
- subject diary check

10.5.3 Ambulatory visits V3 (Day 7), V4 (Day 14), V5 (Day 28, EOS) (multidose phase)

During V3, V4 and V5 the following study procedures will be done:

- vital signs (blood pressure, heart rate, temperature and respiratory rate)
- blood sampling for pharmacokinetic determination
- safety laboratory analysis

	Study Title	Bioavailability Study of COQUN ORAL FORMULATION (CoQ10) administered in Healthy Adults (CoQ10-01)		
	Study ID	VF-BAQ10/2018	Sponsor:	VISUFARMA SpA
	Date	March 03, 2018	Vers.	Final

- record of concomitant medication
- adverse events
- subject diary check

End of study (EOS) is foreseen on Day 28, at 4 weeks after entering the multidose phase.

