10.6.16 Subject restrictions during the study

During informed consent review at screening and at each study visit, subjects will be informed and reminded of the following restrictions:

- No strenuous physical exercise (e.g., weight training, aerobics, football), sunbathing or sauna bathing for 7 days before dosing until after the end-of-study evaluation.
- No alcohol for 72 hours before dosing until after the end-of-study evaluation.
- No consumption of foods or beverages that contain grapefruit 7 days before dosing until after the end-of-study evaluation.
- Intake of xanthine (e.g., caffeine) containing food or beverages must be discontinued 24 hours before dosing. Consumption of such foods and beverages (i.e., coffee, tea, soda, chocolate) or poppy seeds is not permitted at any time while the subjects are hospitalized. If a violation occurs during the domicile period, it must be noted in the source documents and CRF.
- No other food will be consumed at any time during hospitalization.
- No concomitant medication throughout the course of the study until after the end-of study evaluation
- Water will not be permitted 1 hour before visit at site.
- Before blood sampling at screening and at each ambulatory visit, the subjects will be required to fast overnight for at least 8 hours before.

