12.6 Statistical Hypothesis

The study aims are to explore, compare and describe the data for research purposes; no hypotheses are pre-specified.

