5.2 Efficacy Analysis

5.2.1 Primary Efficacy Analysis

The primary objective of this study is to evaluate the best dosage between 100mg once daily or 100mg twice daily for COQUN ORAL FORMULATION in order to reach a level of plasma concentration which might assure its antioxidant effect if taken on a regular basis.

The following pharmacokinetic properties will be evaluated:

- Area under the curve (microg/ml x h)
- C_{max}
- T_{max}
- Elimination half-life (t_{1/2})

Collected Variables

- Plasma concentration of coenzyme Q10 [CRF – Visit 2, 3, 4, 5]

	Form	Form No.	1M-DMST-011-01-A1
	Statistical Analysis Plan	Page	Page 21 of 69
		Effective Date	07/05/2018

Derived Variables

Derived variables are shown in Image 1 and are the following^[2,3]:

- AUC_t
The area under the plasma concentration curve to the last quantifiable concentration (C_t) at time t (AUC_t) will be determined by linear trapezoidal rule. The trapezoidal rule is a method used to numerically approximate the area under the concentration by time curve obtained by summing the area of all trapezoids constructed under the curve. Each trapezoid's area is obtained as:

$$\frac{(C_i + C_{i+1}) * (T_{i+1} - T_i)}{2}$$

where C_i is the concentration at time i (where i is any timepoint before the last observed timepoint T_t), C_{i+1} is the concentration at the following timepoint, T_i is the timepoint i and T_{i+1} is the following timepoint.

- C_{max}
Maximum concentration in the plasma (C_{max}) is obtained directly from the data being the highest plasma concentration value.
- T_{max}
 T_{max} is the collection time in which the maximum concentration is observed and is related to the drug absorption speed.
- $t_{\frac{1}{2}}$
The terminal half-life is defined as the time required for the plasma concentration of a drug to decrease 50% in the final stage of its elimination; this parameter is computed with the formula^[2]:

$$t_{\frac{1}{2}} = \frac{\ln 2}{\lambda_z}$$

where λ_z is the smallest elimination rate constant observed which is obtained as the ratio of clearance and volume of distribution. Clearance is calculated as the ratio of dose and AUC while volume of distribution is obtained as dose divided by concentration at time 0 that is the concentration registered after the first intake of coenzyme (in the single dose time 0 is hour 1, in the multidose phase time 0 is visit 2).

[figure not shown]

Image 1. Pharmacokinetic parameters

	Form	Form No.	1M-DMST-011-01-A1

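### Single-dose AUC and Cmax are computed on raw CoQ10 concentrations, so they mix the endogenous level with absorption; the OD vs BID comparison could also gain precision by using V2 as a covariate

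*SAP*

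**What the plan says.** - Protocol 6.1 states that CoQ10 "is an endogenous molecule, synthesized by our body" and that "Many factors can affect the Q10 blood level of people who are not taking a Q10 supplement", naming age, diet, disease and medication.
- CoQ10 is measured before the single dose (Protocol 10.6.11; SAP 4.3 and 5.2.3). The protocol flow chart leaves the pharmacokinetics row blank at moment 0, but those sections settle the matter. SAP 4.4 names hour 0 and V2 as the baselines of the two phases.
- SAP 5.2.1 obtains AUC_t by the linear trapezoidal rule on measured concentrations, and Cmax "is obtained directly from the data being the highest plasma concentration value". SAP 5.2.3 refers back to these rules for the single dose.
- Protocol 7.2 lists "Area under the curve (microg/ml x h): ≥ 5" and a Cmax of at least 0.8. SAP 5.2.3 repeats both for the single dose. Neither says whether total or baseline-corrected values are meant.
- Baseline is used for concentrations only. Tables 15 and 27 give percent change, Table 25 shows hour 0, and Listing 24 lists concentrations by subject and time point. Tables 16, 17 and 28 and Listings 17 and 25 contain no corrected parameter.
- On the multidose phase, Protocol 9.6 says: "After the screening visit, subjects will have one week of wash-out period, then will be requested to return to the site for V2". Randomisation takes place at that visit. Group B's capsules are "to be taken after lunch and after dinner" (10.5.2) and group A's after dinner. Section 10.6.16 adds: "Before blood sampling at screening and at each ambulatory visit, the subjects will be required to fast overnight for at least 8 hours before". V2 blood therefore precedes randomised dosing.
- The groups are compared by an unpaired t-test without V2 (SAP 5.2.1, Table 17). The only model has gender, time and their interaction. Protocol 12.6 says that "no hypotheses are pre-specified".

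**The concern.** SAP 5.2.3 presents the single-dose phase as the bioavailability analysis. That phase has one arm and no untreated profile, so hour 0 is its only internal reference. Total AUC0-12 and Cmax cannot by themselves show how much CoQ10 came from the capsule. A subject with a high endogenous level and no absorption could exceed both thresholds.

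The multidose point is smaller. V2 is collected, is named as baseline and precedes randomised dosing, but the OD vs BID comparison does not use it as a covariate. With 12 subjects per arm, any correlation between V2 and later levels is precision left unused.

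**Working it through.** The plan gives no power or sample-size figure to reproduce.

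**1. What the endogenous level adds (single dose).** Samples at 0, 1, 2, 4, 8 and 12 h give trapezoid weights 0.5, 1, 1.5, 3, 4 and 2 h, which sum to 12. A constant level b adds 12b to AUC and b to Cmax. With no absorption:

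| b (µg/ml) | AUC0-12 | AUC ≥5 | Cmax ≥0.8 |
|---|---|---|---|
| 0.20 | 2.4 | no | no |
| 0.4 | 4.8 | no | no |
| 0.417 (= 5/12) | 5.0 | yes | no |
| 0.5 | 6.0 | yes | no |
| 0.8 | 9.6 | yes | yes |
| 1.0 | 12.0 | yes | yes |

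The 0.20 is the level at birth (Protocol 6.1), the only endogenous figure in the documents. The subjects are 35 to 75 years old, so every adult value here is an assumption. The Cmax threshold is read as µg/ml, because SAP 5.2.3 prints the AUC unit for it.

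For an assumed absorbed AUC of 2.4, the endogenous share of total AUC is 12b/(12b + 2.4). That is 50% at b = 0.2, 75% at 0.6 and 83% at 1.0.

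**2. What correction does to noise.** Assume independent noise of SD s per sample, a flat true profile and no absorption.
- Total AUC: SD = s√(0.25 + 1 + 2.25 + 9 + 16 + 4) = s√32.5 = 5.7s.
- Corrected AUC (AUC minus 12 × H0): the H0 weight becomes 0.5 − 12 = −11.5. SD = s√(132.25 + 32.25) = s√164.5 = 12.8s per subject, or 12.8s/√24 = 2.6s for the mean of 24. Its expected value is 0.
- Across subjects, corrected AUC varies less than total AUC once the between-subject SD of the endogenous level exceeds s√(132/144) = 0.96s.
- Corrected Cmax (highest of H1 to H12 minus H0) averages +1.16s, or +1.27s if H0 may itself be the maximum. The SAP definition does not exclude H0.
- Setting negative differences to 0 point by point would give corrected AUC a mean of 11.5 × √2·s/√(2π) = +6.5s.

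**3. V2 as covariate (multidose AUC_t).** Weights at days 0, 7, 14 and 28 are 3.5, 7, 10.5 and 7 days, so V2 already carries 3.5/28 = 12.5% of AUC_t, as area and not as an adjustment. I simulated 20,000 trials with 12 per arm and lognormal levels. Assumed inputs: V2 mean 0.8 µg/ml, CV 50% or 30%, and equal correlation between visits. The levels 2.5 (OD) and 3.5 (BID) come from Protocol 6.1, and I assumed they hold in full from Day 7.

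| Correlation | CI width, ANCOVA / t-test (CV 50%) | CV 30% |
|---|---|---|
| 0 | 1.02 | 1.02 |
| 0.3 | 0.93 | 0.92 |
| 0.5 | 0.81 | 0.80 |
| 0.7 | 0.64 | 0.64 |

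If later visits correlate 0.7 with each other but V2 correlates less with them, the gain shrinks. The ratio is then about 1.03 at 0, 0.98 to 0.99 at 0.2, 0.96 at 0.3 and 0.84 at 0.5.

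As an illustration of power under all of these assumptions, CV 50% and equal correlation 0.3 give 57% (t-test) and 63% (ANCOVA). If levels instead rise to 50%, 75% and 100% of target at V3, V4 and V5, the figures are about 49% and 55%. ANCOVA rejected in 4.7 to 4.9% of runs under no difference, and its estimate was at most about 2% below the true difference.

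**The case against.** **Baseline is not ignored.** Percent change against hour 0 is tabulated at every single-dose time point, and a reader could derive a corrected AUC from Listing 24. This stands. The gap is the absence of a pre-specified corrected parameter, not of baseline data.

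**The correction has its own assumption.** Subtracting H0 over 12 hours treats one fasting sample as constant. Protocol 6.1 says diet affects levels, and 10.6.15 serves dinner at around 20:00 on Day -7. Drift from food or time of day is not removed, and there is no untreated profile to estimate it. This stands and has to be stated beside the result.

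**The thresholds decide nothing.** No success rule is attached to them, Table 28 has no threshold row, and no hypothesis is pre-specified. A reader might infer that the study would falsely declare bioavailability. The documents do not support that, because they give neither an adult level nor a decision rule.

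**The t-test is valid.** A reader might infer that leaving out V2 biases OD vs BID. It does not: groups are randomised at V2, so with complete data the contrast is unbiased. An unadjusted test is a legitimate choice in an exploratory study, and the gain from ANCOVA depends on a correlation that no document gives.

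**Conclusion.** The single-dose point holds and does not depend on assumed figures: AUC_t and Cmax as defined combine endogenous level and absorption, and the thresholds do not say which is meant. The crossing points of 0.417 and 0.8 µg/ml follow from the sampling times and a flat profile. Whether subjects of this age lie above them cannot be judged from the documents. Total concentration remains relevant to the primary objective of reaching a plasma level, so totals should stay.

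The multidose point is an optional gain in precision, not an error. Its size rests on assumed correlations, and any power figure rests also on an assumed V2 mean, CV and immediate attainment of 2.5 and 3.5 µg/ml. The check covered AUC_t only, so nothing is claimed for the other parameters in Table 17.

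SAP 5.2.1 treats V2 as time 0, registered after first intake, while SAP 4.4 treats it as baseline. That conflict concerns the half-life formula and should be reconciled as a separate point.

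**What to change.** 1. **SAP 5.2.3, Table 28, Listing 25.** Beside the totals, report H0-corrected AUC0-12 (AUC_t minus H0 × observed time) and H0-corrected Cmax (highest of H1 to H12 minus H0). Do not set negative values to 0. State whether ≥5 and ≥0.8 refer to total or corrected values. Read absorption mainly from corrected AUC, since noise alone pushes corrected Cmax upward. Give two caveats with it: H0 is assumed constant over 12 h, and assay noise per subject rises from 5.7s to 12.8s.
2. **SAP 5.2.1, Table 17.** Compare OD and BID on AUC_t by ANCOVA with V2 as covariate, and show the unadjusted t-test result beside it. Note that V2 follows the single dose by a week, so it is a pre-multidose level and purely endogenous only if wash-out is complete.

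The cost is SAP wording and a few columns. The samples are already planned. ANCOVA uses one degree of freedom, which costs about 2% of interval width if V2 proves uninformative.

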3. ANALYSIS SETS AND SUBGROUPS

3.1 Analysis sets

The following analysis sets will be considered in this study.

Safety Set

This set consists of all randomized subjects who sign informed consent and take at least one dose of study product.

Intention-to-treat Population

This set contains all randomized subjects.

Per Protocol Population

The per protocol population consists of all subjects who meet all inclusion/exclusion criteria and who do not have any major protocol deviation.

The primary endpoint will be evaluated on ITT and PP populations. Results obtained on the PP population will be considered as supportive of those obtained on the ITT set.

Secondary endpoints and safety assessment will be evaluated on the Safety set.

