4.3 Visit Names and Labels

The names to be used in the analysis datasets and the labels to be used in the tables, listings and figures for the different study visits are defined below.

Visit number	Visit name	Visit label, which appear in TLFs
V1-H0	Visit 1: assessment moment 0 (before COQUN intake)	Visit 1 – Hour 0
V1-H1	Visit 1: assessment hour 1	Visit 1 – Hour 1
V1-H2	Visit 1: assessment hour 2	Visit 1 – Hour 2
V1-H4	Visit 1: assessment hour 4	Visit 1 – Hour 4
V1-H8	Visit 1: assessment hour 8	Visit 1 – Hour 8
V1-H12	Visit 1: assessment hour 12	Visit 1 – Hour 12
V2	Visit 2 - Day 0	Visit 2
V3	Visit 3 - Day 7	Visit 3
V4	Visit 4 - Day 14	Visit 4
V5	Visit 5 - Day 28 (EOS)	Visit 5

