5.1.3 Protocol Violations

Protocol violations are major deviations from the procedures outlined in the protocol like for example missed evaluations, incorrect timing of evaluations, non-compliance with study medications and intake of medications not allowed or any non-adherence to the protocol that impacts subject's rights, safety or welfare.

Protocol violations are defined as any deviations that may affect the efficacy outcome or the treatment of the subjects. All potential protocol violations will be discussed and reviewed on a case-by-case basis. A decision will be made as to the effect of the possible violations to determine if it is considered major or minor. The status, major or minor, of each potential protocol violation will be tabulated. A subject may have one or more major protocol violations resulting in the exclusion of that subject from the per protocol analysis set.

Collected Variables: Not applicable

Derived Variables:

- protocol violation category
- type of violation (descriptive free text)
- details of violation (descriptive free text)

Imputations for missing values: Not applicable

Analysis Sets to be used for:	Tables	ITT analysis set
	Listings	ITT analysis set
	Figures	Not applicable

Protocol violations will be summarized by treatment group as follows:

Table 8. Major/Minor Protocol Violations (ITT set) The number of all subjects with at least one major or minor protocol violation, will be presented by treatment group. For all categories of major and minor protocol violations, default frequency tabulation will be presented. Subjects may have more than one major/minor protocol violation.

Subjects data listings will include:

Listing 6. Minor and Major Protocol Violations A by-subject listing of all subjects with their minor and major protocol violations will be presented.

	Form	Form No.	1M-DMST-011-01-A1
	Statistical Analysis Plan	Page	Page 16 of 69
		Effective Date	07/05/2018

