	Statistical Analysis Plan	Page	Page 22 of 69
		Effective Date	07/05/2018

Analysis of Primary Efficacy variable:

Descriptive statistics such as mean \pm standard deviation, median with interquartile range, minimum, maximum and coefficient of variation will be presented for the plasma concentration of coenzyme Q10 at each time point in the entire sample of subjects. 95% confidence interval will be provided as well.

An explorative analysis on gender will be performed showing descriptive statistics for plasma concentration of coenzyme Q10 by gender. The effect of gender will be explored by means of a mixed model for repeated measures with covariates *gender*, time and the interaction term *gender*time*.

Descriptive statistics will be also provided for the plasma concentration of coenzyme Q10 at each time point by treatment group.

Change of plasma concentration versus baseline (i.e. change versus visit 2 values) will be computed for each study visit both for the whole sample and by treatment group.

Change will be computed in the following way:

$$\text{Change (\%)} = \frac{\text{Value at Visit X} - \text{Baseline Value}}{\text{Baseline Value}} \times 100$$

Area under the curve, maximum concentration in the plasma, time of maximum concentration and terminal half-life will be presented descriptively on the original scale.

95% confidence interval will be provided for the means of 100mg OD and 100mg BID for COQUN ORAL FORMULATION for the parameters AUC_t , C_{max} , T_{max} and terminal half-life. A Student t-test for unpaired data will be performed in order to detect differences between the two groups in the pharmacokinetics parameters.

A concentration by time graph will be presented for the multidose phase by treatment group in order to have a graphical visualization of the pharmacokinetics properties over time.

Line graphs will be provided for the concentration of coenzyme Q10 in the whole sample and by gender.

In performing statistical analysis, it is important to assess the statistical outliers. In fact, inclusion or exclusion of outlying subjects may lead to a different conclusion in assessment of differences in bioavailability between two formulations. It is therefore important to identify these outliers and study their effects.

Primary endpoint will be evaluated on the ITT population and analysis will be replied on the PP population. Results obtained on the PP population will be considered as supportive of those obtained on the ITT set.

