	Mean (SD)	X.XXX (XX.XX)	X.XXX (XX.XX)	X.XXX (XX.XX)
	95% CI	XX.X/XX.X	XX.X/XX.X	XX.X/XX.X
	CV (%)	XX.XX	XX.XX	XX.XX
	Median	X.XXX	X.XXX	X.XXX
	Interquartile			
	Range	XX.X	XX.X	XX.X
	Min/Max	XX.XX/XX.XX	XX.XX/XX.XX	XX.XX/XX.XX

N: Number of subjects in specified treatment group

n: Number of subjects with data available

SD = Standard deviation

CV = Coefficient of Variation

RUN: DDMMYYYY HH:MM <1MED > Page X of Y

Table 17. Confidence Interval and Results of T-test for Primary Efficacy Variable (ITT Analysis Set)

Parameter	Mean	95% Confidence Interval		Difference between the means of the two groups	P-value
		Lower Limit	Upper Limit		
AUC_t	X.XX	X.XX	X.XX	X.XX	X.XXXX
C_max	X.XX	X.XX	X.XX	X.XX	X.XXXX
T_max	X.XX	X.XX	X.XX	X.XX	X.XXXX
t_(1/2)	X.XX	X.XX	X.XX	X.XX	X.XXXX

Notes:

P-values are referred to a Student t-test comparing means of the two groups. A p-value less than 0.05 indicates a statistically significant difference.

RUN: DDMMYYYY HH:MM <1MED > Page X of Y

	Form	Form No.	1M-DMST-011-01-A1
	Statistical Analysis Plan	Page	Page 47 of 69
		Effective Date	07/05/2018

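### Multidose Tmax can only be a visit day, ITT AUC_t shrinks with early dropout, and Table 17 lacks a between-arm V5 contrast and any CI for a difference

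*SAP*

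**What the plan says.** The primary objective (protocol 7.1, SAP 2.1) is to choose between 100 mg OD and 100 mg BID by the plasma level reached on regular intake. Protocol 12.7 names AUC, Cmax, Tmax and half-life as the primary variables. Protocol 12.6 states no hypotheses.

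SAP 5.2.1 takes the multidose concentrations from V2, V3, V4 and V5. The protocol flow chart, SAP 4.3 and the Table 13 shell carry one value per visit, and hour labels exist only for V1. Protocol 10.6.9 and 10.6.16 require a fast of at least 8 hours before these samples.

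From these values the SAP derives:
- AUC_t: "The area under the plasma concentration curve to the last quantifiable concentration", by the linear trapezoidal rule.
- Cmax: the highest observed value.
- Tmax, which "is the collection time in which the maximum concentration is observed and is related to the drug absorption speed".
- Half-life: ln 2 divided by clearance over volume, with AUC in the clearance and the V2 concentration in the volume.

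The between-arm analysis is then: "A Student t-test for unpaired data will be performed in order to detect differences between the two groups in the pharmacokinetics parameters". The Table 17 shell has rows for these four parameters only. Its columns are a mean with 95% limits, the difference between the group means and a p-value, and its note reads "P-values are referred to a Student t-test comparing means of the two groups".

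The ITT definition is "This set contains all randomized subjects", and missing values are not imputed. The analysis is repeated on PP: "Results obtained on the PP population will be considered as supportive of those obtained on the ITT set". Tables 13 and 15 summarise concentration and percent change by visit within each arm. The only repeated-measures model has gender, time and their interaction, with no treatment term.

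**The concern.** These are the usual definitions for a densely sampled dosing interval, applied to four samples spread over four weeks.

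- A Tmax read from weekly or fortnightly fasting samples says at which visit the level was highest. It carries no information on absorption speed.
- An area that stops at the last available sample is comparable between subjects only if all of them are sampled to the same day.
- The V5 level, after 28 days of regular intake, is the value closest to the primary objective, but it is only described arm by arm.

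At stake are one uninformative test, one comparison (with the half-life row that depends on it) that unequal early dropout can bias, and an OD/BID conclusion reported without an interval for the difference.

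**Working it through.** The plan gives no power, SD or dropout figure to reproduce. The check applies the SAP's own definitions.

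**Inputs from the documents.** Sampling at 0, 168, 336 and 672 h; expected levels of about 2.5 (OD) and 3.5 (BID) ug/ml (protocol 6.1); 12 subjects per arm; Table 17 threshold 0.05, taken as two-sided.

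**Assumptions.** V2 level 0.8 ug/ml. Levels either plateau by day 7 or rise through 70%, 85% and 100% of the V5 level. Between-subject CV 25-35%, 10% noise, lognormal, 20,000 simulated trials.

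**Tmax.** The only possible values are 0, 168, 336 and 672 h. If both arms have the same profile shape, the t-test rejects in 2-5% of trials, whatever the difference in level.

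**AUC_t.** Each segment is (C_i + C_{i+1})/2 × (T_{i+1} − T_i). For BID under the plateau:
- to day 7: (0.8 + 3.5)/2 × 168 = 361.2
- to day 14: 361.2 + 3.5 × 168 = 949.2
- to day 28: 949.2 + 3.5 × 336 = 2125.2

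| Profile | Arm | To day 7 | To day 14 | To day 28 | Day 7 / day 28 | Day 14 / day 28 |
|---|---|---|---|---|---|---|
| Plateau | OD | 277.2 | 697.2 | 1537.2 | 18.0% | 45.4% |
| Plateau | BID | 361.2 | 949.2 | 2125.2 | 17.0% | 44.7% |
| Rising | OD | 214.2 | 539.7 | 1316.7 | 16.3% | 41.0% |
| Rising | BID | 273.0 | 728.7 | 1816.5 | 15.0% | 40.1% |

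**BID/OD ratio of mean AUC_t (plateau).**
- Complete: 2125.2 / 1537.2 = 1.38.
- One BID subject last sampled on day 7: (11 × 2125.2 + 361.2)/12 = 1978.2, ratio 1.29 (rising: 1.28).
- Two such subjects: (10 × 2125.2 + 2 × 361.2)/12 = 1831.2, ratio 1.19 (rising: 1.18).
- One such OD subject instead: (11 × 1537.2 + 277.2)/12 = 1432.2, ratio 2125.2 / 1432.2 = 1.48.
- One BID dropout with a replacement: (12 × 2125.2 + 361.2)/13 = 1989.5, ratio 1.29. Replacement under protocol 8.4 does not remove the short area from ITT.

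**Half-life.** Clearance/volume = (dose/AUC)/(dose/C_V2) = C_V2/AUC, so t1/2 = ln 2 × AUC / C_V2. Under the BID plateau this is 0.693 × 2125.2 / 0.8 = 1841 h for a completer and 0.693 × 361.2 / 0.8 = 313 h for a day-7 dropout. It shrinks by the same factor as the area.

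**Simulated power of the comparison (ranges over CV and profile).**

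| BID subjects last sampled on day 7 | ITT AUC_t | Cmax | Cmax ratio |
|---|---|---|---|
| 0 | 60-87% | 59-85% | 1.40 |
| 1 | 25-41% | 50-84% | 1.36-1.39 |
| 2 | 4-5% | 41-83% | 1.33-1.38 |

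One BID subject last sampled on day 14 leaves AUC_t power at 38-65%. Log V5 in subjects who reach V5 (plateau, CV 25% to 35%, no V2 adjustment) has power of 84% to 61% with complete data, 82% to 59% with one BID subject missing and 81% to 57% with two.

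**The case against.** Several points on the other side stand.

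- **A level is already compared.** A reader might infer that Table 17 has no between-arm comparison of level. That is not so. Multidose Cmax is the highest visit concentration, its row has a difference and a p-value, and the working shows that it resists early dropout fairly well.
- **No dropout rate is given.** A reader might infer that the AUC_t test is bound to lose power. The loss needs at least one of 12 healthy volunteers in an arm to leave early in a 28-day study, and the large figures put every dropout in the BID arm. The direction of bias follows from the definitions, but its size is assumed.
- **The Tmax test is mostly uninformative, not usually misleading.** It rejects in 88% of trials only if OD has reached plateau by day 7 while BID rises through 70/85/100%. A milder mismatch (BID at 90/95/100%) gives 24%. Nothing in the documents suggests different shapes by arm.
- **V5 is not named in the objective**, and protocol 12.7 lists other primary variables. A V5 contrast therefore belongs beside them, not in their place.
- **Partial safeguards exist.** SAP 5.1.3 says "Protocol violations are major deviations from the procedures outlined in the protocol like for example missed evaluations, incorrect timing of evaluations", so a truncated subject may leave PP. If so, AUC_t power stays at 59-85% with one such subject. However, major status is decided case by case, SAP 3.3 plans no data review, and PP is only supportive. SAP 5.2.1 asks for outliers to be studied but gives no method. Protocol 8.4 asks for the final visit on discontinuation, but protocol 10.7 lists no CoQ10 sample there, and the area would still end early.
- **Serial sampling.** Protocol 10.6.11 could be read as hourly samples at each ambulatory visit. The flow chart, SAP 4.3, Table 13 and Listing 16 all show one value per visit.

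**Conclusion.** The point holds in three parts.

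1. Multidose Tmax is a visit day whatever the data. The statement on absorption speed is wrong for this phase, and the test does not inform the dosage choice.
2. ITT AUC_t, and the half-life built on it, are biased against the arm that loses more subjects early. The sizes shown rest on the assumed profiles, V2 level, CVs and dropout. With complete data AUC_t ranks the arms about as well as V5 does.
3. Table 17 compares a level through Cmax but has no contrast at V5 and no confidence interval for any between-arm difference.

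Cmax itself needs only a clearer label. In an exploratory study without hypotheses this should be fixed but does not invalidate the trial. An estimate with an interval would serve the objective better than four p-values.

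**What to change.** In SAP 5.2.1 and the affected shells (Tables 16 and 17, Listing 17):

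- Drop the multidose Tmax t-test, or relabel the variable as visit of highest concentration, and delete the absorption-speed statement for this phase.
- Relabel multidose Cmax as highest visit concentration.
- Compute AUC, and any half-life based on it, only over a fixed 0-28 day window in subjects with a V5 sample, as supportive.
- Add to Table 17 the BID/OD ratio of geometric mean V5 concentration, adjusted for V2, beside the protocol 12.7 parameters. Give it the 90% CI that protocol 12.1 provides for. At 12 per arm the unadjusted 90% half-width is 1.717 × √(2/12) = 0.70 SD.
- Support it with a repeated-measures model of log concentration with treatment, time and treatment-by-time, the form already used for gender.
- Record the change in SAP section 6.

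The cost is text and shells, before the SAP is signed ahead of hard lock. No new samples are needed.

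The downsides should be stated. Subjects without V5 enter only the repeated-measures model. The restricted AUC conditions on staying in the study. The complete-case V5 ratio can be biased if dropout depends on level. When the BID subject with the highest or lowest day-7 level left (plateau, CV 25% and 35%, 800 trials per scenario), the complete-case ratio was 1.33-1.35 or 1.46 against a true 1.40. The model gave 1.39-1.41, and ITT AUC_t gave 1.24-1.25 or 1.33 against 1.38-1.40 without dropout. The two V5 results should be read side by side whenever a V5 value is missing.
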